6.8.2 Laboratory Parameters

For microbiological analysis, incidence of pathogen by source and in total will be evaluated. For routine laboratory, descriptive analysis will be performed. Analysis of daily assessed data will be performed over the following time frames: Screening / 6h after randomization / Day 1 / Day 2-7 / Day 8-28.

6.8.3 Other Safety Data

Descriptive analysis

Clinical parameters: body temperature, respiratorical frequency, hemodynamic parameters (SAP, MAP, DAP, CVP, CO) will be analyzed descriptively over time.

For anti-infective therapy and adjunctive sepsis therapy, incidence analysis will be performed.

For intensive care measures (intubation, central venous catheter, arterial catheter, renal replacement therapy, ventilation, ECMO, hemodynamic monitoring), frequencies will be presented.

Analysis of daily assessed data will be performed over the following time frames: Screening / 6h after randomization / Day 1 / Day 2-7 / Day 8-28.

6.9 Subgroup Analysis

Descriptive analysis of 90 day mortality and Kaplan Meier analysis will be given in subgroups for

Baseline-albumin (0..< 20g/l, 20..<25 g/l, 25..<30 g/l, $\geq 30g/l$)

Baseline-lactate (< / ≥ 8mmol/l, stratum of randomization)

SOFA baseline value (0..<10, 10..<15, ≥15)

SAPS II baseline value (0..<40, 40..<80, ≥80)

APACHE II baseline value (0..<10, 10..<20, 20..<30, ≥30)

If predefined cuts lead to any small subgroups (less than 10 patients), analysis using quartiles of study population for subgroup definition will be added for the respective parameter.

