of the albumin therapy (within 6 h or 6-24 h after the onset of severe sepsis). The study showed no outcome difference between the study groups. Nevertheless, the results of the study gave two interesting signals: firstly, there was a tendency for a potential survival benefit of albumin therapy in patients who started therapy 6-24 h after onset of sepsis compared to those who started it earlier (relative risk of 90-day mortality = 0.9; 95% confidence interval: 0.81-1.05, p = 0.2). Secondly, in the 1121 patients with septic shock, 90-day mortality was lower in the albumin group (564 patients) than in the non-albumin group (43.6 vs. 49%, p = 0.03). Additional post-hoc analyses in various study subgroups confirmed a potential survival benefit in patients with increased disease severity (according to arterial blood pressure, lactate levels or SvO2 on randomization) (unpublished data). Taken together, the current evidence suggests that albumin administration in patients with severe and advanced sepsis who have potential impairment of the protective effects of serum albumin may provide a survival benefit. However, no prospective, randomised trial has adequately studied this hypothesis in patients with septic shock.

The aim of the ARISS study is to investigate the effect of albumin administration and maintenance of a serum albumin concentration of at least 30 g/l for 28 days after onset of septic shock compared to volume replacement therapy without albumin on patient survival. The hypothesis is that albumin administration started within 6-24 hours after the onset of septic shock aimed at maintaining a serum albumin concentration of at least 30 g/l for 28 days after the onset of septic shock will reduce 90-day all-cause mortality in these patients compared to volume replacement therapy without albumin.

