11.2 Randomisation

Randomisation will be stratified according to:

- Serum lactate levels within 24 h before inclusion in the trial: ≤ 8 mmol/l vs. > 8 mmol/l and
- centre

in the treatment groups

- albumin group
- control group without albumin

Albumin administration will be adjusted after the starting dose according to serum albumin concentrations. Therefore, blinding will not be possible.

Group assignment will be determined using a validated electronic tool (PaRANDies) after inclusion of the patient. Randomisation will be based on a randomisation list created in advance with nQuery Advisor 7.0.

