11.3.3 Subgroup analyses

The primary endpoint and selected secondary endpoints (SOFA, organ failure defined as SOFA organ failure score ≥ 2) will be described for the following subgroups:

Baseline lactate ≤ 8 mmol/L versus> 8 mmol/L

SOFA total and subscores, SAPS II, APACHE II: by baseline quartiles

Details of the statistical analyses will be described in the Statistical Analysis Plan.

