6.6 Primary Analysis

The primary efficacy variable 90 day mortality will be analyzed with a Generalized mixed model with fixed effects SAPS II score, baseline lactate, baseline-albumin-serum value, type of admission (surgical/non-surgical) and treatment group and random effect center; descriptive statistics will be presented. The primary analysis will take place in FAS according to ITT-principle; an additional sensitivity analysis in PPS will be performed. In addition, descriptive analysis of 90-day mortality in subgroups with respect to baseline-lactate, baseline albumin, baseline SOFA, SAPS II und APACHE II will be performed.

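### SAP 6.9 only describes 90-day mortality in 16 subgroup cells, with no effect estimate, interval or treatment-by-subgroup interaction, so a chance reversal in a cell could not be judged

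*SAP*

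**What the plan says.** The three places that deal with subgroups of the primary endpoint agree with each other.

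- SAP 6.9: "Descriptive analysis of 90 day mortality and Kaplan Meier analysis will be given in subgroups for" baseline albumin, lactate, SOFA, SAPS II and APACHE II, each with fixed cut-points. If any cell has fewer than 10 patients, a quartile version is added for that factor.
- SAP 6.6: "descriptive analysis of 90-day mortality in subgroups with respect to baseline-lactate, baseline albumin, baseline SOFA, SAPS II und APACHE II will be performed".
- Protocol 11.3.3: the endpoints "will be described for the following subgroups", with details left to the SAP.

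SAP 6.2 defines descriptive output for non-metric data as counts and percentages, by treatment group and in total. The primary model in SAP 6.6 has "fixed effects SAPS II score, baseline lactate, baseline-albumin-serum value, type of admission (surgical/non-surgical) and treatment group and random effect center". These are main effects only, and SOFA and APACHE II are not among them. The exploratory between-group tests in protocol 11.3.2 cover secondary endpoints, not subgroups of 90-day mortality.

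Two passages bear on why subgroups matter here. Protocol 2.1 reports that post-hoc analyses of an earlier albumin trial "confirmed a potential survival benefit in patients with increased disease severity", with lactate one of the severity markers named. Protocol 11.2 ("Randomisation will be stratified according to") lists lactate and centre.

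**The concern.** Tables of mortality by arm within severity bands invite the reader to compare the arm difference in one band with that in the next. Such a comparison needs a contrast between subgroups and a measure of its uncertainty. The plan supplies neither, only percentages and curves. With 16 cells, some of them probably small, a cell in which albumin looks worse, or unusually good, can easily arise when the effect is the same in everyone. The report would then contain a striking cell with no planned way to tell it from noise. Any test would have to be chosen after the result had been seen.

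**Working it through.** **Inputs.** Protocol section 11 (Sample size) gives control mortality 50%, albumin mortality 42.5%, two-sided 5% level, 80% power, 706 per arm and 1412 in total. The synopsis gives 42% for albumin. I use 42.5% because it is the figure that reproduces the sample size. SAP 6.9 gives the cell counts. Cell shares are assumed.

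**The plan's own figure.** The two-proportion formula gives n = [1.96·√(2·0.4625·0.5375) + 0.8416·√(0.25 + 0.425·0.575)]² / 0.075² = 693 per arm, or 1386 in total, and 1438 with continuity correction. The stated 1412 lies between them. A simulated Mantel-Haenszel test over 50 centres with the stated heterogeneity has 80.9% power at 706 per arm. A 42% rate gives 1218 (1266 with continuity correction), which does not match.

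**Reversal in one cell.** With n patients per arm in a cell, SE = √(0.494375/n), where 0.494375 = 0.25 + 0.425·0.575, and P(albumin looks worse) = Φ(−0.075/SE).

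| Patients in cell | P(reversal) |
|---|---|
| 706 | 2.3% |
| 471 | 5.1% |
| 353 | 7.8% |
| 282 | 10.3% |
| 141 | 18.5% |
| 50 | 29.7% |
| 10 | 40.6% |

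**Any of the 16 cells.** With equal cells within each factor, the expected number of reversals is 8·0.078 + 6·0.051 + 2·0.023 = 0.98. The five factors divide the same patients, so the chance of at least one reversal has to be simulated. The simulation takes the same risk within each arm for every patient.

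| Assumed shares (albumin; lactate; SOFA; SAPS II; APACHE II), % | At least one reversal |
|---|---|
| Equal within each factor | 48–50% |
| 15/30/35/20; 80/20; 35/50/15; 15/70/15; 5/30/40/25 | 66–67% |
| 35/35/20/10; 80/20; 40/45/15; 15/70/15; 5/25/45/25 | 66–70% |

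Correlation between the factors changes these figures little. For lactate alone at an assumed 80/20 split, the chance that either cell reverses is only about 11% (0.6% for 1130 patients plus 10.3% for 282). Most of the risk comes from the smaller cells of the other factors.

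**What an interaction test could add.** Take a two-level factor with share f in one level, on the risk-difference scale. Then SE = √[0.494375/(706f) + 0.494375/(706(1−f))], and the interaction detectable with 80% power is 2.80·SE.

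| Split | SE (points) | Power for 7.5 points | Detectable with 80% power |
|---|---|---|---|
| 50/50 | 5.3 | 29% | 14.8 points |
| 30/70 | 5.8 | 26% | 16.2 points |
| 20/80 | 6.6 | 21% | 18.5 points |
| 10/90 | 8.8 | 14% | 24.7 points |

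For 80% power at 7.5 points with equal halves, about 4 × 1386 = 5544 patients would be needed. Five independent tests at 5% have a family-wise error of 1 − 0.95⁵ = 22.6%.

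**The case against.** The strongest reply is that the plan makes no subgroup inference. All three passages say the subgroups are described, no subgroup test is planned, and SAP 6.11 fixes the cut-points for the three scores in advance in place of quartiles, which limits data-driven selection. This stands as far as it goes: the plan licenses no claim of effect modification. It does not help a reader faced with a reversed cell, since counts and percentages carry no measure of uncertainty for the arm difference. Kaplan-Meier output may include intervals for each curve. The SAP does not ask for them, and they would not address the difference between arms or between subgroups.

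A reader might infer that the trial sets out to test whether sicker patients benefit more, and that the SAP leaves its own hypothesis unanswered. The documents do not support this. Protocol 2.1 uses the severity signal to motivate studying septic shock. The hypothesis there and the objectives in protocol 3.1 and 3.2 concern the effect in the whole population. Stratifying by lactate also serves prognostic balance and does not by itself pose a question about effect modification.

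A reader might also infer that a misleading reversal is certain, or that an interaction test would resolve the matter. Under the assumptions above, 30–50% of trials show no reversal at all. A forest plot would display the same chance reversals, though with intervals, and interaction power is low. Both limits belong in the SAP text.

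**Conclusion.** The gap is real and modest. Mortality is described by arm in 16 cells with nothing planned to judge differences between them. Under a uniform effect, at least one reversed cell is expected in about half of trials with equal cells and about 66–70% with skewed cells. These figures rest on the planning rates, 1412 evaluable patients, the same risk in every cell within an arm, and assumed cell shares. The primary analysis and its conclusion are not affected. Interaction terms and intervals are the better method and use data already collected. They would make the imprecision visible, but could detect only interactions of about 15–25 points with 80% power.

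**What to change.** Amend SAP 6.9 before the data are analysed.

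1. For each factor, lactate stratum first, fit the primary mixed model with that factor's main effect and a treatment-by-factor term. Add the main effect for SOFA and APACHE II, which the model lacks. For SAPS II, lactate and baseline albumin, state whether the categorised factor replaces or joins the existing covariate.
2. For the interaction test, use continuous or ordered terms for albumin, SOFA, SAPS II and APACHE II. Keep the fixed cut-points for display.
3. Report subgroup odds ratios with 95% confidence intervals and the interaction p-values in one forest plot, labelled exploratory and not adjusted for multiplicity. State the low power and the family-wise error of up to about 23% across five independent tests.
4. Define the lactate subgroup by the stratum actually used at randomisation. The SAP has "Baseline-lactate (< / ≥ 8mmol/l, stratum of randomization", while protocol 11.2 and 11.3.3 put a value of exactly 8 mmol/l in the lower group. The two should be reconciled.

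The cost is SAP wording and five extra model fits, with no new data or patients. The downside is that a non-significant interaction may be misread as proof of a uniform effect, and an isolated significant one as proof of a differential effect. The exploratory label and the intervals guard against both.

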6.10 Interim Analysis

Not planned

6.11 Deviation from Protocol and Amendment

Corresponding to recommendations of reviewers, subgroups with respect to SOFA, SAPS II and APACHE II baseline values are prespecified instead of using quartiles.

7 Software and Validation

Analysis will be performed with SAS Version 9.4 or higher.

Validation plan:

All programs will be validated on either a basic or an enhanced validation level. Basic validation level means validation by the programmer according ZKS Jena SOP Bi06 and includes check of program code, check of log-file and check of output. Enhanced validation will be performed by an independent programmer and includes enhanced check of program code, log-file and output. Primary efficacy analysis will be validated by independent duplicate programming. Results of adverse events analysis will be cross-checked with the contents of the safety data base.

Programms for DSUR and SMC reports will be validated on basic validation level by the respective programmer.

Analysis	Validation level
Population characteristics and baseline data	basic
Previous and concomitant diseases and therapies	basic
Exposition to therapy / compliance	basic
Primary analysis	enhanced
Secondary analyses	basic
Adverse events	basic
Laboratory parameters	basic
Other safety data	basic
